1.3.1.3 Non-Clinical Studies

Wuis studied the PK of racemic baclofen and the R- and S-enantiomers in dogs after IV infusions of 2 mg/kg of the racemate and 1 mg/kg of each enantiomer. Blood samples were collected at selected times for 25 hours after drug administration, and urine was collected for a period of 50 hours. Taking into account the small number of animals (n=3), the PK parameters of the racemate and individual enantiomers were comparable.

Blood-brain barrier transport profiles of racemic baclofen, STX209, and S-baclofen were assessed in rats using unit impulse response methodology. Although plasma and cerebral spinal fluid (CSF) elimination kinetics did not differ between STX209 and S-baclofen, there was a suggestion of stereoselective transport of baclofen across the blood-brain barrier with STX209 transported more efficiently.

In a subsequent study, quantitative electroencephalography (EEG) parameters in conjunction with plasma concentration measurements and PK-pharmacodynamic (PD) modeling techniques were used to characterize both the PD and plasma-effect site equilibration kinetics of baclofen. This study again found similar PK for STX209 and S-baclofen. The rate constant for transport of STX209 into the CSF was 2-fold higher than for S-baclofen, but there was no difference in rate constants out of the

CSF, and there was no PK interaction between the 2 isomers with respect to transport into the CSF. The net result was that times for the CSF to reach 50% equilibrium were equivalent for racemic baclofen, STX209, and S-baclofen. PD parameters for the R-isomer were not different from the parameters of the racemate, indicating that PD interactions between the R and S-isomers do not occur. Furthermore, the equilibration rate constants at the effect site were comparable after administration of the racemate or individual enantiomers.

The plasma and brain pharmacokinetics of STX209 was also evaluated in the mouse. In one study (STX-REP-0011), plasma and brain concentrations of STX209 were determined in C57BL/6 mice dosed at three doses of STX209 (1, 3 and 6 mg/kg) administered as intraperitoneal injections twice daily for 9 days. Dose-related increases in plasma and brain exposure were observed, with a rapid t_{max} in both tissues (0.25-0.5 hr) and short terminal elimination half-lives (< 2 hr). Low brain-to-plasma concentration ratios were also observed (≤ 0.11 up to 2 hr; 0.16-0.28 at 8 hr).

STX209 brain and plasma levels were compared to those produced following administration of racemic baclofen in C57BL/6 mice. Animals were administered STX209 (1, 3 or 6 mg/kg) or racemic baclofen (2, 6 or 12 mg/kg) via intraperitoneal injection and brain/plasma levels of each enantiomer were measured at intervals up to 240 minutes. Blood plasma levels of R-baclofen were higher in mice administered 2x racemic baclofen compared to those receiving STX209. Conversely, R-baclofen levels in brain were higher in mice treated with STX209 compared to those receiving 2x racemic baclofen. Consistent with this, brain-to-plasma ratios of R-baclofen were higher in animals receiving 1 and 3 mg/kg STX209 than in animals receiving 2 and 6 mg/kg racemic baclofen.

In summary, these results indicate that the PK and PD properties after administration of the single isomer, STX209, are similar to those observed when STX209 is administered with S-baclofen as a racemic mixture.

1.4 Selection of Drugs and Dosages

This is a study examining the acute effect of STX209 on brain activity at two different doses: 15mg and 30mg. Subjects will receive STX209 via oral disintegrating tablets, administered in individual 15mg tablets. Over a period of three visits, participants will receive a single randomly administered dose of placebo and in order from smallest to largest a single-dose of STX209 (15mg, and 30mg). All visits subjects will receive two tablets in the following order, with placebo randomly administered:

Dosage	Tablets Administered
15mg	One 15mg tablet of STX209 and one placebo
30mg	two 15mg tablets STX209 and zero placebo
Placebo	Zero STX209 tablets and two placebo

Across the three visits, all subjects will receive all doses, with the subject blind to dose.

1.5 Compliance Statement

This study will be conducted in full accordance with all applicable Children's Hospital of Philadelphia Research Policies and Procedures and all applicable Federal and state laws including IND 21 CFR 312 and regulations. All episodes of noncompliance will be documented.

The investigators will perform the study in accordance with this protocol, will obtain consent (Appendix 1) and assent, and will report unanticipated problems involving risks to subjects or others in accordance with The Children's Hospital of Philadelphia IRB Policies and Procedures and all federal requirements. Collection, recording, and reporting of data will be accurate and will ensure the privacy, health, and welfare of research subjects during and after the study.

2 STUDY OBJECTIVES

A candidate therapeutic for ASD has been developed – STX209, a GABA-B agonist (made available to this project by the Clinical Research Associates, LLC (CRA)). Since this pharmaceutical targets synaptic activity that have clear electrophysiological correlates, one goal of this proposal is to assess the responsiveness (sensitivity to change) of MEG measures to acute administration of STX209 at various doses in adolescents on the autism spectrum. The study also aims to establish the nature of the putative relationship between such electrophysiologic markers and GABA and glutamate levels using MEGAPRESS spectrally-edited magnetic resonance spectroscopy (MRS), which we have previously used to demonstrate a relationship between GABA concentration and gamma oscillatory activity (Gaetz et al. [8]).

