2.1 Primary Objective (or Aim)

1. To determine whether STX209 produces a significant change in MEG target parameters compared to baseline as well as compared to placebo treatment. Secondly, to determine if the magnitude of such change is influenced by STX209 dose: 0mg (placebo) versus 15mg versus 30mg.
2. To determine whether STX209 leads to a significant change in MRS-obtained auditory cortex GABA levels compared with placebo treatment. Secondly, to determine whether the magnitude of the GABA change is influenced by STX209 dose level.
3. To determine if dose-dependent changes in MEG target parameters are correlated to dose-dependent changes in MRS target parameters in auditory cortex.

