5.6 Statistical Methods

Primary statistical analyses assess baseline versus post acute-dose (placebo, STX209 15 and 30 mg) changes for (1) M100 auditory latency, and (2) post-stimulus auditory gamma-band activity. For each dependent measure, ANOVAs with dose as a repeated measure will examine baseline versus post acute-dose changes (analyses showing no significant differences across time in baseline M100 and gamma measures will allow use of a single averaged baseline measure). Contrasts of *a priori* interest assess (1) a baseline versus post-acute dose change in the dependent measures averaging across STX209 15 and 30 mg, as well as (2) a change in dependent measures from baseline versus STX209 15 mg versus STX209 30 mg, with this test demonstrating an effect of dose. Secondary and exploratory analyses examine baseline to post acute-dose response changes in MRS auditory GABA concentration as well as associations between MEG functional measures and MRS GABA concentration.

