5.6.2 Efficacy Analysis

Our principal hypotheses relate to baseline to STX administration changes in the latency of the auditory M50, M100 and MMF responses, and gamma-band total power and inter-trial coherence (examined pre- and post-stimulus). To this end, for each dependent measure, ANOVAs with dose as a repeated measure will examine baseline versus post acute-dose changes (analyses showing no significant differences across time in baseline M50, M100, MMF and gamma measures will allow use of a single averaged baseline measure). Contrasts of *a priori* interest assess (1) a baseline versus post-acute dose change in the dependent measures averaging across STX209 15 and 30 mg, as well as (2) a change in dependent measures from baseline versus STX209 15 mg versus STX209 30 mg, with this test demonstrating an effect of dose. For the secondary endpoints, associations between MRS GABA/Cr ratios and the MEG dependent measures will be assessed using Pearson correlation analyses.

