5.7 Sample Size and Power

Forty individuals with ASD (aged 14 to 18 years) will be recruited. In each individual, baseline and post acute-dose imaging data will be obtained at three doses: (1) placebo, (2) STX209 15 mg, or (3) STX209 30 mg. Imaging measures at these three doses will be obtained at least 1 week apart, with the order of placebo and STX209 pseudo-randomized with the constraint that the STX209 15mg dose will be administered before the STX209 30 mg dose (FDA requirement). Assuming lost data or incomplete data sets from 4 individuals, the following power calculations were performed assuming a final sample of 36. As detailed in Section 1.3, given significant between subject variability in auditory cortex neural circuit pathology and thus potential between subject differences with regard to normalization of brain activity in response to STX209, the below statistical analyses conservatively assume a response to STX209 from approximately 50% of the participants. As detailed below, although the study is sufficiently powered to assess a baseline versus a 'general' post acute-dose change (i.e., averaging 15mg and 30mg), there is insufficient data to determine if the study is powered to observe a difference between STX209 15mg and STX209 30mg acute dose brain responses. As such, present data will provide preliminary data to guide future studies investigating STX209 dose differences.

Regarding the primary aims, assuming baseline to post acute-dose changes in M100 latency of approximately 2.5 ms (5 ms = one-half the ASD and control group differences reported in Roberts et al. (2010) and in the range observed in the single Arbaclofen study patient (2-8ms), but half of 5 ms given acute responses in only 50% of the participants), and assuming a standard deviation of similar size (which may be conservative given initial cross-dose averaging), and assuming a response in only 50% of the population, given a sample of 36 and $p = 0.05$, the power to detect a main effect on M100 latency is equal to 0.80. Assuming baseline to post acute-dose changes in post-stimulus gamma-band activity approximately half that reported in Edgar et al. (2015), the power to detect a main effect on gamma activity is approximately 0.70.

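### Responsiveness of the MEG measures is a stated goal, but the analysis plans no placebo-adjusted effect estimate, confidence interval or repeatability estimate for any of them

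*Combined protocol and SAP*

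**What the plan says.** Section 2 describes one goal as to "assess the responsiveness (sensitivity to change) of MEG measures to acute administration of STX209 at various doses". Section 2.1 puts this into practice as a question of detection, "To determine whether STX209 produces a significant change in MEG target parameters compared to baseline as well as compared to placebo treatment", and then asks "to determine if the magnitude of such change is influenced by STX209 dose".

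For the analysis, Section 5.6.2 states that "ANOVAs with dose as a repeated measure will examine baseline versus post acute-dose changes". Section 5.6 lists placebo among the post-dose conditions, so placebo is a level of the dose factor. The first a priori contrast in both sections is "a baseline versus post-acute dose change in the dependent measures averaging across STX209 15 and 30 mg". The second sets baseline against 15 mg and 30 mg. Placebo appears in neither.

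Each visit has a pre-dose recording and a recording 60 minutes after dosing (Table 1 note; Section 4.3). Each boy therefore supplies three undosed recordings and one placebo pre/post pair. On the three baselines, Section 5.6 says that "analyses showing no significant differences across time in baseline M100 and gamma measures will allow use of a single averaged baseline measure". Baseline values are also the reference for the post-dose change and supply the median split in Section 5.7.

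Descriptive summaries are promised only for baseline and demographic characteristics (Section 5.6.1). The one planned measure of association is a Pearson correlation of the MEG measures with GABA/Cr (Section 5.6.2). On dose, Section 5.7 says that "present data will provide preliminary data to guide future studies investigating STX209 dose differences".

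**The concern.** Sensitivity to change is a matter of degree: how large the drug-related change is, and how that compares with the noise of the measure. The plan asks whether a change is significant, and a p-value mixes size of change with sample size.

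Two things are at stake. First, a pre/post contrast on drug alone cannot separate a drug effect from whatever else happens over the hour between recordings, such as fatigue, habituation to the stimuli or settling in the scanner. The placebo visit is there to separate them, and Section 2.1 promises that comparison, but neither named contrast makes it. Second, later dose studies will need an effect estimate with its uncertainty and a noise SD. If these are not pre-specified, they may go unreported, or the index may be chosen after the results are seen.

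**Working it through.** **1. The plan's own figure.** The nearest stated number is the M100 power of 0.80 (Section 5.7). Inputs from that section: n = 36, mean change 2.5 ms, SD of similar size, alpha 0.05 (taken here as two-sided). For a paired t-test, d = change/SD, noncentrality = d√n, df = 35 and critical t = 2.030.

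| Reading of the SD | d | d√36 | Power |
|---|---|---|---|
| 2.5 ms | 1.00 | 6.00 | 0.9999 |
| Half respond by 5 ms, half by 0: √(2.5² + 2.5²) = 3.54 ms | 0.71 | 4.24 | 0.985 |
| 5 ms | 0.50 | 3.00 | 0.83 |
| Back-solved for power 0.80: 5.21 ms | 0.48 | 2.88 | 0.80 |

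At n = 36, none of the readings tried gives 0.80 from the stated inputs. (18 subjects with an SD of 3.54 ms would give 0.807, but the text does not say this.) The gamma power of about 0.70 comes with no effect in units and no SD, so it cannot be checked. The documents therefore do not fix a standardised change, and the values below are assumptions.

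**2. What a significant result says about size.** The 95% CI for a standardised change comes from inverting the noncentral t with t = d√36.

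| Observed standardised change | t | 95% CI |
|---|---|---|
| 0.34 (smallest significant: 2.030/6) | 2.03 | 0.00 to 0.67 |
| 0.48 | 2.88 | 0.13 to 0.82 |
| 1.00 | 6.00 | 0.59 to 1.40 |

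All three are significant, yet they describe very different degrees of response.

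**3. What the averaging check says about repeatability.** It is an F-test of mean differences across visits. If the mean does not drift, its false-positive rate is 5% whatever the within-subject noise. In a simulation of 36 subjects with three baselines (4,000 runs per setting), the share passing was 94.6% at ICC 0.1, 95.4% at ICC 0.5 and 94.6% at ICC 0.9. Passing shows only that no mean drift was detected.

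**4. What the collected data could give at n = 36.**
- Between-visit within-subject SD from three baselines: 36 × 2 = 72 df. The CI factors are √(72/χ²), giving 0.86 to 1.19 times the estimate.
- ICC from three baselines: an estimate of 0.5 has CI 0.30 to 0.68; 0.7 has 0.55 to 0.82; 0.9 has 0.83 to 0.94.
- Within-session SD of change from the placebo pair: 36 − 1 = 35 df, giving 0.81 to 1.30 times the estimate by the same formula.

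**5. Which noise applies.** The baselines lie 4 to 14 days apart (Sections 3.1.3 and 4.3), so they measure between-visit noise. The endpoint is a change over about an hour within one session. The placebo pre/post pair measures noise on that scale.

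**The case against.** The strongest reply is that the goal is addressed. Section 2 calls responsiveness one goal among others, and Section 2.1 makes it operational as change against baseline and placebo and by dose. The synopsis labels the study exploratory for MEG. Placebo is a level of the ANOVA dose factor, so the omnibus test does use it. For a single-degree-of-freedom pre/post contrast, t/√n is the standardised change, so an effect size can be recovered afterwards. All of this stands. It makes the problem one of pre-specification. It does not supply the missing placebo contrast, nor any estimate that the plan commits to report.

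A reader might infer more than the documents support:
- *That the trial cannot say how responsive a measure is.* It can. The recordings needed are collected, and step 4 shows usable precision.
- *That the baselines serve only the averaging decision.* They are also the comparator for change and the basis of the median split. The narrower statement holds: they are compared with each other only for averaging.
- *That the plan calls a measure responsive when p < 0.05 and unresponsive otherwise.* No section states such a rule.
- *That M100 and gamma will be ranked by which one reaches significance.* No objective or analysis compares the measures.
- *That the assumed SD in Section 5.7 results from this gap.* That SD is an assumption made before this trial's data exist, so it is not a result of how those data will be analysed.

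**Conclusion.** The point holds as a gap in the analysis text. Responsiveness and a placebo comparison are promised. What is planned is ANOVA tests and two contrasts against baseline, with no placebo-adjusted estimate, no interval and no repeatability estimate for any MEG measure. The averaging check cannot fill the last gap.

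The size of the loss cannot be stated as one number, because the documents give no usable standardised change: the stated inputs imply about 1.0, while the stated power implies about 0.48. At n = 36 these would carry 95% CIs of 0.59 to 1.40 and 0.13 to 0.82. The calculations assume 36 complete subjects, roughly normal change scores and two-sided 0.05.

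This does not invalidate the design. It is a correction worth making before the data are analysed, because it answers an aim that the protocol already states.

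**What to change.** In Sections 5.6 and 5.6.2, for M100 latency and post-stimulus gamma:

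1. Make the placebo-adjusted change the basis of the responsiveness conclusion: (post minus pre on drug) minus (post minus pre on placebo), at 15 mg, at 30 mg and pooled, each with a 95% CI. Give its standardised response mean (mean divided by the SD of the placebo-adjusted change) with a CI. Use each visit's own pre-dose recording. If one averaged baseline is subtracted at every visit, it cancels and leaves only post-drug minus post-placebo.
2. As supporting results, report the between-visit within-subject SD and ICC from the three pre-dose recordings, and the within-session SD of change from the placebo pair. The last is the noise relevant to a 60-minute change.
3. The ANOVAs can stay.

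Cost: a few lines of text and no new visits, recordings or subjects. The price is wider intervals. Let each visit's pre/post change have SD s, with correlation ρ between visits and the same true response in every boy. The pooled change against baseline then has variance s²(1 + ρ)/2, and the placebo-adjusted pooled change has 1.5s²(1 − ρ). The SD ratio is √[3(1 − ρ)/(1 + ρ)]: 1.73 at ρ = 0, 1.34 at ρ = 0.25 and 1.00 at ρ = 0.5. The documents give no ρ, so this is a range. Section 5.7 should say that its power refers to the change against baseline and not to the placebo-adjusted change.

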2.1 Primary Objective (or Aim)

1. To determine whether STX209 produces a significant change in MEG target parameters compared to baseline as well as compared to placebo treatment. Secondly, to determine if the magnitude of such change is influenced by STX209 dose: 0mg (placebo) versus 15mg versus 30mg.
2. To determine whether STX209 leads to a significant change in MRS-obtained auditory cortex GABA levels compared with placebo treatment. Secondly, to determine whether the magnitude of the GABA change is influenced by STX209 dose level.
3. To determine if dose-dependent changes in MEG target parameters are correlated to dose-dependent changes in MRS target parameters in auditory cortex.

3 INVESTIGATIONAL PLAN

3.1 General Schema of Study Design

3.1.1 Screening Phase

Screening - Contact Prior to Visits to CHOP

Determination of eligibility will be conducted over the phone after the parent has provided verbal informed consent. This phone screen determines eligibility, and only subjects who meet study inclusion and exclusion criteria will be enrolled in this study.

Pre-Visit Intake Questionnaire

The Pre-Intake Questionnaire is completed with a parent over the phone once a subject is deemed eligible for this study and wishes to participate. The parent is given the option of completing the short questionnaire immediately after the phone screen or scheduling a separate time to complete it

over the phone with one of the study staff. The purpose of the questionnaire is to provide the study staff with additional necessary information for scheduling, as well as information that will help the staff best prepare for the subject's visits. The hope is that both visits are positive experiences and that we can maximize compliancy. Therefore this questionnaire should be completed via phone prior to the subject's first study visit.

Once potential subjects have been identified, via a phone interview the study will be described. If potential subjects are interested, then they will be schedule for Visit 1. At this first visit the study will again be described and if the subject is still interested they consent for signed.

3.1.2 Screening Visit:

The screening visit for the study will be conducted at the Children's Hospital of Philadelphia and will entail the following procedures:

- Written informed consent provided by parent and child assent if appropriate
- Neuropsychological evaluation, including clinical and behavioral testing (*only if applicable*)
- Physical Examination (*include abdominal palpation to assess for liver enlargement, assessing for decreased tone and postural problems, increased drooling and poor orofacial tone, problems holding head up, and difficulty with coordination of motor actions*), Height and Weight, and Medical/Surgical History Review
- Vital Signs: Temperature, Blood Pressure, Heart Rate, and Respiratory Rate
- Blood Draw (BUN and Creatinine): *Arbaclofen (STX209) is eliminated in the urine, BUN and Creatinine are done to confirm that subject has normal urinary function.*

Neuropsychological Evaluation: Clinical and Behavioral Assessments

On the screening visit, clinical and behavioral testing will be performed to confirm diagnosis of autism spectrum disorder and to evaluate language function. Intelligence testing will be performed to obtain an IQ estimate. The following instruments will be used:

- ADOS-2 (Autism Diagnostic Observation Schedule- 2nd edition)- *A clinical tool that looks at a child's language, social skills and behavior. This updated version is attached to the eIRB application section 12.02 (2.0).*
- ADI-R (Autism Diagnostic Interview-Revised) [parent interview]- *A parent interview that is used to look at autism symptoms. The interview asks about a child's language, social skills and behavior.*
- CBCL (Child Behavior Checklist) [parent report]- *This is a parent completed rating scale that asks about behaviors like attention problems, aggression, anxiety, and depression.*
- CELF –IV (Clinical Evaluation of Language Fundamentals- 4th edition)- *This tool evaluates a child's language understanding and expression. This updated version is attached to the eIRB application section 12.02 (2.0).*
- Intervention History Form- *This form is based on one created for the NIH funded autism research network (CPEA: Collaborative Programs of Excellence for Autism). Our revised version is attached in the eIRB application section 12.02 (2.0). It was created by an expert panel of autism treatment researchers from throughout the country, so as to capture*

information about past treatments. This information can be an important moderating influence on the developmental trajectory of each child.

- SCQ (Social Communication Questionnaire-Lifetime version) [parent completed measure]- *This is a parent completed rating scale that asks about a child's social and communication skills both over the span of the child's lifetime.*
- SRS-II (Social Responsive Scale, 2nd edition) [parent completed measure]- *This is a parent completed rating scale that asks about a child's social development*
- Vineland Adaptive Behavior Scales (2nd edition) [Parent/Caregiver Rating Form]- *This is a parent completed measure used to support the diagnoses of intellectual and developmental disabilities.*
- WASI-II (Wechsler Abbreviated Scale of Intelligence (2nd edition)) - *This is a standardized tool that measures a child's problem-solving and reasoning skills.*

Tests will not be administered if results from recent testing (less than 12 months prior to screening visit) are available (data from tests will only be used if subjects who previously participated in one of our approved research studies, agreed to share their data on future studies). Depending on the availability of previous test results it is anticipated that behavioral and cognitive test duration will be between 1 and 4 hours. The ADI-R parent interview will be administered as needed when further information about ASD symptoms is required (e.g., when children with no prior ASD diagnosis have screened positive on the other autism diagnostic measures). The parent will be told during the child's screening visit if we would like to do the ADI-R interview. The interview will then be conducted during the child's first imaging study visit.

Testing will be performed in the Division of Child Development, Children's Seashore House, Dept. of Radiology, Roberts Center for Pediatric Research [name] at Specialty Care at [name] .

In the case that a standing ASD diagnosis is called into question during the neuropsychological evaluation, the neuropsychological report will document that the child's prior ASD diagnosis received in the community cannot be confirmed. The psychologist who did the child's testing will also contact the subject's parent via phone to discuss the results. The diagnostic information is obtained for research purposes only, and is not sufficient for a clinical diagnosis, therefore the psychologist will provide appropriate referral information if the parent wishes to pursue further clinical evaluation. These results will not affect any educational, medical, or special services that the child might currently be receiving. It will be up to the participant or family to accept, use or reveal this information. Results from this testing will not appear in the subject's medical record.

In the case that there are any additional concerns following a child's neuropsychological evaluation, the psychologist will document the concerns in the written report as well as speak to the parent via phone. Again, appropriate referral information will be provided if the parent wishes to pursue further evaluation, since the diagnostic information obtained is not sufficient for a clinical diagnosis. Results from this testing will not appear in a subject's medical record.

